3.6. Study Completion

The study will be complete when all patients have discontinued study medication and have been followed to progression, death, withdrawal, or have been lost to follow-up or 1 year after the last patient receives their first dose of study treatment, whichever is first. All patients should be followed for progression and survival until the study is complete. Patients who are still being treated at the completion of the study and are deriving benefit may continue treatment under a separate continuation protocol.

Premature termination of this clinical trial may occur because of a regulatory authority decision, change in opinion of the IRB/IEC, drug safety problems, or at the discretion of Pfizer. In addition, Pfizer retains the right to discontinue development of AG-013736 at any time.

Regardless of the reason for termination, all data available for the patient at the time of discontinuation of follow-up must be recorded in the CRF. All reasons for discontinuation of treatment must be documented.

In terminating the study, the investigators will ensure that adequate consideration is given to the protection of the patient's interest.

4. STUDY TREATMENTS

4.1. Allocation to Study Treatment

All patients will receive AG-013736.

4.2. Drug Supplies

4.2.1. AG-013736 Dose

The initial dose of AG-013736 will be 5 mg BID administered orally. Doses should be taken as close to 12 hours apart as possible and at approximately the same times each day. Instructions for modifying doses in individual patients can be found in Section 4.2.6.

Patients must be instructed that if they vomit anytime after taking a dose, that they must not "make it up" with an extra dose, but instead resume subsequent doses as prescribed. Any missed dose may be taken up to 3 hours prior to the next scheduled dose, otherwise it should be skipped. All missed or vomited doses should be recorded in the source documents and CRFs.

4.2.2. AG-013736 Formulation and Packaging

AG-013736 will be supplied as 1-mg and 5-mg tablets for oral administration. The tablets are film coated.

4.2.3. AG-013736 Preparation and Dispensing

AG-013736 will be dispensed in opaque plastic bottles to protect the compounds from light.

4.2.4. Compliance

Patients will maintain diaries to include missed or changed doses. Pill counts on returned AG-013736 bottles of drug should be performed.

4.2.5. AG-013736 Drug Storage and Accountability

AG-013736 will be supplied for the study by the Pharmacy Operations Office, Pfizer Global Research and Development. Clinical Trial Material (CTM) will be shipped to the study site with an Investigational Drug Receipt Confirmation form. This form will be completed with protocol number, drug name, lot number, quantity received and condition upon receipt. A copy of the form must be returned via fax to the Pharmacy Operations Office within 24 hours of receipt. A copy will also be returned via mail.

The investigator, or an approved representative (eg, pharmacist), will ensure that all study drug is stored in a secured area, under recommended storage conditions and in accordance with applicable regulatory requirements. Drug should be stored at controlled room temperature (15-30°C), avoiding exposure to light.

To ensure adequate records, all study drug will be accounted for in the case report form and drug accountability inventory forms as instructed by Pfizer. Unless otherwise authorized by Pfizer, at the end of the clinical trial all drug supplies unallocated or unused by the subjects must be returned to Pfizer or its appointed agent (eg, a contract research organization).

AG-013736 is considered a hazardous drug (due to possible reproductive toxicity), and should be handled according to the recommended procedures described in the current edition of the American Society of Hospital Pharmacists (ASHP), Technical Assistance Bulletin on Handling Cytotoxic and Hazardous Drugs, American Hospital Formulary Service (AHFS) Drug Information (1999) and its references. Procedures described in each institution's pharmacy or hospital standard operating procedure manual should be followed when handling hazardous drugs.

4.2.6. Dose Interruptions and Modification

4.2.6.1. Dose Interruption and Reduction

Adverse events and other symptoms will be graded according to the current Common Terminology for Adverse Events version 4.0 (CTCAEv4) (see URL: http://ctep.cancer.gov/reporting/ctc.html). This section contains management of adverse events except hypertension, hemoptysis and proteinuria that are discussed in subsequent sections.

Patients developing a treatment-related CTC Grade 2 adverse event that is subjectively intolerable (except alopecia) and cannot be controlled by supportive treatment will have their dosing interrupted and then re-started at the same dose after resolution to CTC Grade ≤1 or baseline. If resolution does not occur within 4 weeks, the patient should be removed from the study.

Patients developing a treatment-related Grade 3 or 4 nonhematologic adverse event (except for alopecia) that cannot be controlled by supportive treatment will have their treatment interrupted. Patients with a treatment-related Grade 4 hematologic adverse event that cannot be controlled by supportive treatment drug will have treatment interrupted. Appropriate follow-up assessments will be done until recovery to less than or equal to CTC Grade 1 or baseline occurs. Upon adequate recovery, treatment can be resumed at a 20% lower dose, rounded down to accommodate dosage form availability. If resolution does not occur within 4 weeks, the patient should be removed from the study.

Any patients with recurring subjectively intolerable toxicity, ie, at least 1-week interruption of treatment for the same adverse event on at least 2 separate occasions, despite optimal supportive care, will resume dosing at a 20% lower dose once adequate recovery is achieved.

If any patient requires more than 2 dose reductions, contact the sponsor for discussion prior to removing the patient from the study. Patients removed from treatment for intolerable toxicity should still be followed for disease progression and survival.

The criteria for dose modification for study drug related adverse events is summarized in the table below:

Protocol: 03/21/16

RELATED ADVERSE EVENTS	INTERVENTION
CTC Grade 2 toxicity that is subjectively	Interrupt dosing; re-start at same dose after resolution to
intolerable (except alopecia) and not controlled by optimal supportive medication	CTC Grade ≤1 or baseline
CTC Grade ≥3 nonhematologic toxicity that is not controlled by optimal supportive medication	Interrupt dosing; re-start at 20% lower dose after resolution to CTC Grade ≤1 or baseline
Grade 4 hematologic toxicity that is not controlled by optimal supportive medication	
Recurrent subjectively intolerable toxicity (at least a week interruption on 2 occasions) that is not controlled by optimal supportive medication	Interrupt dosing; re-start at 20% lower dose after resolution to CTC Grade ≤1 or baseline

Guidelines for dose reductions for specific adverse events are provided in the following sections.

4.2.6.2. AG-013736 Dose Reduction for Hypertension

Patients treated with AG-013736 will be followed every two weeks in the clinic to monitor blood pressure. Patients will also be instructed to measure their blood pressure (BP) at home when feasible. All blood pressure measurements will be recorded in a diary and brought to the nurse or study coordinator at each clinic visit. Patients will be counseled by the study staff to inform their doctor immediately when their blood pressure parameters meet any of the limits outlined below or if they develop symptoms perceived to be related to elevated BP (eg, headache, visual disturbance).

New or additional antihypertensive therapy (see Section 4.3, Concomitant Medication(s) for guidance) should be started if 2 blood pressure readings, separated by at least 1 hour, show the following: 2 systolic blood pressure readings greater than 150 or 2 diastolic blood pressure readings greater than 100 mm Hg. Alternately, the dose of existing antihypertensive medication(s) may be increased. Furthermore, the early initiation of antihypertensive agents for Grade 1 and Grade 2 hypertension in order to minimize the occurrence of more severe or persistent hypertension while undergoing treatment with AG-013736 will not constitute a Grade 3 toxicity.

Patients on maximal antihypertensive treatment (eg, 4 antihypertensive medications given for 2 weeks) who have 2 systolic blood pressure readings, separated by at least 1 hour, greater than 160, or 2 diastolic blood pressure readings, separated by at least 1 hour, greater than 105, will have treatment with AG-013736 held. (Note: if study drug is held, patients receiving antihypertensive medications should be monitored closely for hypotension.) Blood pressure

measurements used for AG-013736-discontinuation decision-making should be done in the clinic. Treatment with AG-013736 may be restarted at approximately 20% lower dose, rounded down to accommodate dosage form availability, after the systolic blood pressure reduces to less than 150 and the diastolic blood pressure reduces to less than 100.

Patients not on maximal antihypertensive treatment who in a 1-week period have 2 systolic blood pressure readings greater than 200 or 2 diastolic blood pressure readings greater than 110, will have treatment with AG-013736 held. (Note: if study drug is held, patients receiving antihypertensive medications should be monitored closely for hypotension.) Blood pressure measurements used for AG-013736-interruption decision-making should be done in the clinic. Treatment with AG-013736 may be restarted at the previous dose after the systolic blood pressure reduces to less than 150 and the diastolic blood pressure reduces to less than 100.

Guidance on dose interruption and reduction for hypertension is summarized in the table below.

HYPERTENSION MANAGEMENT PLAN				
Degree of Blo	ood Press	ure Elevation	Management	
Systolic Pressure		Diastolic Pressure		
2 BP readings separated by at least 1 hour show systolic pressure >150 mm Hg	OR	2 BP readings separated by at least 1 hour show diastolic pressure >100 mm Hg	Maintain dose of study drug; patient to self monitor blood pressure. Institute new or additional antihypertensive medication or increase dose of current medication	
2 BP readings separated by at least 1 hour show systolic pressure >160 mm Hg in patients on maximal antihypertensive treatment	OR	2 BP readings separated by at least 1 hour show diastolic pressure >105 mm Hg in patients on maximal antihypertensive treatment	Interrupt dosing; once BP is less than 150/100 restart drug at 20% lower dose	
2 BP readings within 1 week show systolic pressure >200 mm Hg in patients who are not on maximal antihypertensive treatment	OR	2 BP readings within 1 week show diastolic pressure >110 mm Hg in patients who are not on maximal antihypertensive treatment	Interrupt dosing; adjust antihypertensive medication; once BP less than 150/100 restart drug at previous dose	

4.2.6.3. AG-013736 Dose Reduction for Hemoptysis

Bleeding from the lungs will be graded according to the Hemorrhage category of CTC.

Treatment with AG-013736 will be discontinued for hemoptysis of Grade 1 or greater. If Grade 1 hemoptysis resolves within 1 week, treatment with AG-013736 may continue at the current dose level. Patients who experience Grade 1 hemoptysis that does not resolve within

1 week or who experience Grade 2 or greater hemoptysis at any time should be taken off study and not receive further AG-013736.

4.2.6.4. AG-013736 Dose Reduction for Proteinuria

At documentation of \geq 2+ proteinuria by dipstick, patients should have a 24-hour urine collection for total protein. Alternatively, the urine protein: creatinine ratio (UPCR) will be evaluated to determine if it is \geq 2. AG-013736 dosing may continue while waiting for the test results.

If <2 g proteinuria/24 hours is reported, or the UPCR is </= 2, patients may continue AG-013736 treatment without dose reduction.

If proteinuria > 2g/24 hours but ≤ 3.5 g/24 hours or a UPC between 2 and 3.5 is reported, treatment with AG-013736 may continue at a 20% lower dose, rounded down to accommodate dosage form availability. A 24-hour urine collection for total protein and creatinine clearance must be performed every 4 weeks to monitor the degree of proteinuria until it has decreased to <2 g/24 hours. Once the urinary protein is below 2 g/24 hours, urine dipstick determinations may be used.

If UPC is >3.5 or the 24 hour urine shows >3.5 g proteinuria/24 hours is reported, treatment with AG-013736 should be suspended. Twenty-four hour urine collection for total protein and creatinine clearance should be done weekly until results show <2 g proteinuria/24 hours, or a UPC <2, at which time treatment with AG-013736 may be restarted at a 20% lower dose, rounded down to accommodate dosage form availability. Patients, once restarted on AG-013736, will have weekly monitoring for proteinuria by semiquantitative testing (eg, dipstick) as long as the proteinuria reading is 2+ or higher, or, alternatively, by quantitative methods as long as proteinuria is \geq 1 g/24 hours. The 24-hour urine collection to monitor the degree of proteinuria should be repeated every 4 weeks until it has decreased to <500 mg/24 hours.

4.2.6.5. Dose Escalation

Patients who tolerate AG-013736 with no adverse events related to AG-013736 above CTC Grade 1 for any consecutive 8-week period should have their dose increased by 20% unless the patient is responding to therapy.

Once a patient has a dose reduction for study drug related toxicity, the dose normally will not be re-escalated. However, patients who tolerate the lower dose without toxicities above Grade 1 for at least 8 weeks may be considered for re-escalation. The investigator and sponsor's medical monitor will discuss the case and decide if re-escalation is appropriate.

Dose escalation to a maximum of 10 mg BID will be considered for patients without an elevation of diastolic blood pressure above 90 mm Hg in Cycle 1 or other significant drug-related toxicities.

4.3. Concomitant Medication(s)

Palliative and supportive care for disease-related symptoms will be offered to all patients on this trial. Low-dose oral steroids (defined as ≤5 mg per day prednisone or equivalent) or topical or inhaled steroids at any dose may be taken during the study. No other chemotherapy, hormonal therapy, radiotherapy, or experimental anticancer medications will be permitted while the patient is on study. Any disease progression requiring other forms of specific anticancer therapy will be cause for discontinuation from study treatment.

In vitro studies with human liver microenzymes and recombinant CYP450 enzymes indicated that AG-013736 metabolism was primarily mediated by the drug-metabolizing enzyme CYP3A, and to a lesser extent by CYP1A2. Additionally, the drug also undergoes N-glucuronidation in liver microsomes of some species. Clinically, there is likelihood that AG-013736 plasma concentrations may be increased in the presence of co-administered potent inhibitors of the CYP3A and glucuronosyltransferase enzymes. The potential exists for drug-drug interactions with CYP3A inhibitors such as grapefruit juice, ketoconazole, miconazole, itraconazole, erythromycin, clarithromycin, verapamil, ergot derivatives, indinavir, saquinavir, ritonavir, nelfinavir, lopinavir, and delavirdine. Caution should be exercised in patients receiving AG-013736 in combination with these and other potent CYP3A inhibitors until appropriate clinical drug interaction studies are performed.

AG-013736 metabolism may be induced in patients taking CYP3A4 or CYP1A2 inducers (carbamazepine, dexamethasone, felbamate, omeprazole, phenobarbital, phenytoin, primidone, rifabutin, rifampin, and St John's wort) and this may reduce AG-013736 plasma concentrations. Patients who require concomitant treatment with CYP3A4 or CYP1A2 inducers are not eligible for the study. Since CYP1A2 is also known to be induced in chronic smokers, there is likelihood that AG-013736 plasma concentrations may be reduced in these individuals.

The ability of AG-013736 to increase concentrations of coadministered drugs was also investigated in studies with human liver microsomes. At expected therapeutic plasma concentrations (0.01 to $1.0 \,\mu\text{g/mL}$), AG-013736 appears most likely to inhibit the drug metabolizing enzymes CYP1A2 and CYP2C8, 2 enzymes not frequently observed as predominant drug metabolizing enzymes. Paclitaxel, theophylline, and tacrine are among the few drugs whose plasma concentrations are likely to be increased by AG-013736.

AG-013736 is highly bound to proteins in human plasma (99.5% bound at concentrations of 0.2 to 20 μ g/mL). Therefore, drug interactions with other agents that are also highly bound to plasma proteins are a possibility.

Patients who need to be on chronic antacid therapy with histamine H₂ antagonists (eg, cimetidine [Tagamet[®]], famotidine [Pepcid[®]], nizatidine [Axid[®]], ranitidine [Zantac[®]]), proton-pump inhibitors (eg, lansoprazole [Prevacid[®]], rabeprazole [Aciphex[®]], pantoprazole [Protonix[®]], and esomeprazole [Nexium[®]]), or locally acting antacids (eg, Maalox[®], Milk of Magnesia[®], Amphojel[®]) should stagger the timing of their AG-013736 and antacid dosing. Patients should avoid use of antacids for 2 hours before through 2 hours after taking AG-013736 tablets. Note, however, that patients taking the proton-pump inhibitor omeprazole (Prilosec[®]) are not eligible

Page 27 of 53

Protocol: 03/21/16

for this study and that patients should not use omeprazole while taking AG-013736 tablets because omeprazole is a CYP1A2 inducer.

AG-013736 is not likely to have drug-drug interactions with commonly used antihypertensive agents belonging to the class of ACE inhibitors including angiotensin II receptor antagonists (enalapril, captopril, losartan, vasartan), beta-blockers (atenolol, metoprolol, labetalol), or diuretics (hydrochlorothiazide, furosemide). Within the class of calcium channel blockers, verapamil, and to a lesser extent nifedipine, nicardipine, and diltiazem have a potential for increasing plasma AG-013736 plasma concentrations, due to CYP3A inhibition and should not be used as first choice in antihypertensive treatment. Other calcium channel blockers (amlodipine, bepridil, felodipine) are less likely to raise AG-013736 plasma levels.

The information on drug interactions is based on preclinical data from studies using human and animal metabolizing enzyme systems. No formal human drug interaction studies have been performed.

All concomitant medications and blood products, as well as interventions (eg, analgesic use or paracentesis) received by patients from the first dose of study drug until the end of study visit will be recorded on the CRF.

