3.2.2. Exclusion Criteria

Subjects with one or more of the following criteria are ineligible for this study:

- 1. Stage IV disease
- 2. History of hemoptysis
- 3. Gastrointestinal abnormalities including:
 - inability to take oral medication
 - requirement for intravenous alimentation
 - prior surgical procedures affecting absorption including gastric resection
 - treatment for active peptic ulcer disease in the past 6 months
 - active gastrointestinal bleeding, unrelated to cancer, as evidenced by hematemesis, hematochezia or melena in the past 3 months without evidence of resolution documented by endoscopy or colonoscopy.
 - malabsorption syndromes.
- 4. Previous treatment with anti-angiogenesis agents including thalidomide, or inhibitors of epidermoid growth factor (EGF), platelet derived growth factor (PDGF), or fibroblast growth factors (FGF) receptors.

Page 16 of 53

Protocol: 03/21/16

- 5. Current use or anticipated inability to avoid use of drugs that are known potent CYP3A4 inhibitors (ie, grapefruit juice, verapamil, ketoconazole, miconazole, itraconazole, erythromycin, clarithromycin, ergot derivatives, indinavir, saquinavir, ritonavir, nelfinavir, lopinavir, and delavirdine).
- 6. Current use or anticipated inability to avoid use of drugs that are known CYP3A4 or CYP1A2 inducers (ie, carbamazepine, dexamethasone, felbamate, omeprazole, phenobarbital, phenytoin, primidone, rifabutin, rifampin, and St. John's wort).
- 7. Active seizure disorder or evidence of brain metastases. (Appropriate imaging should be done to rule out brain metastases.)
- 8. A serious uncontrolled medical disorder or active infection that would impair their ability to receive study treatment.
- 9. History of a malignancy (other than melanoma) except those treated with curative intent for skin cancer (other than melanoma) or in situ breast or cervical cancer or those treated with curative intent for any other cancer with no evidence of disease for 5 years.
- 10. Major surgical procedure or any radiation therapy within 4 weeks of treatment, minimum rest period is 28 days post surgery; maximum rest period 56 days post surgery.
- 11. Dementia or significantly altered mental status that would prohibit the understanding or rendering of informed consent and compliance with the requirements of this protocol.
- 12. Patients (male and female) having procreative potential who are not using adequate contraception or practicing abstinence.

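### Section 4.3 leaves verapamil open as a later-line antihypertensive during axitinib dosing, although exclusion 5 keeps patients who use it out of the trial

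*Combined protocol and SAP*

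**What the plan says.** **Entry.** Section 3.2.2, exclusion 5, makes ineligible anyone with "Current use or anticipated inability to avoid use of drugs that are known potent CYP3A4 inhibitors (ie, grapefruit juice, verapamil, ketoconazole" and the rest of a list of 14 entries.

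**Reason.** Section 4.3 says that "AG-013736 plasma concentrations may be increased in the presence of co-administered potent inhibitors of the CYP3A" and glucuronosyltransferase enzymes, and names the same 14 as examples of CYP3A inhibitors with which an interaction is possible.

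**On treatment, all 14.** Section 4.3 continues: "Caution should be exercised in patients receiving AG-013736 in combination with these and other potent CYP3A inhibitors", until clinical interaction studies have been done.

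**On treatment, antihypertensives.** Section 4.2.6.2 says that "New or additional antihypertensive therapy (see Section 4.3, Concomitant Medication(s) for guidance) should be started" once two readings at least an hour apart exceed 150 mm Hg systolic or 100 mm Hg diastolic. The guidance it points to says that verapamil, and less strongly nifedipine, nicardipine and diltiazem, may raise axitinib levels "due to CYP3A inhibition and should not be used as first choice in antihypertensive treatment". It then adds: "Other calcium channel blockers (amlodipine, bepridil, felodipine) are less likely to raise AG-013736 plasma levels".

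**Evidence base.** Section 4.3 also states: "The information on drug interactions is based on preclinical data from studies using human and animal metabolizing enzyme systems". It says that no formal human interaction studies have been done.

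**The concern.** Exclusion 5 looks forward as well as at current use: expecting that a patient could not avoid a drug matters only if the drug is meant to be avoided on study. The rule that governs treatment is weaker than that intention. Caution presupposes that the combination may occur, and a drug that is merely not first choice may still be second, third or fourth. A patient could therefore be given verapamil on treatment after passing an entry criterion that would have refused them for taking it.

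This lies on a foreseeable clinical path. Section 1.2 reports hypertension as the phase 1 dose-limiting toxicity and as the most frequent related event of grade 3 or higher, at 14%. Sites will be starting and adding antihypertensives, and Section 4.3 is where they are told to look. What is at stake is patient safety: treating axitinib-related hypertension with a drug that may raise axitinib levels.

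**Working it through.** The plan states no figure on this point. The check compares the texts and makes a few counts.

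**1. Are the two lists the same?** Exclusion 5: grapefruit juice (1) + verapamil (1) + azoles (3) + macrolides (2) + ergot derivatives (1) + antiretrovirals (6) = 14. The Section 4.3 list also has 14 entries. Compared as sets they are identical, with no entry in one and missing from the other.

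**2. What is the on-treatment rule for those 14?**

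| | Entry (3.2.2, item 5) | During dosing (4.3) |
|---|---|---|
| All 14 inhibitors | Not eligible | Caution |
| Verapamil for hypertension | Not eligible | Not first choice |

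Express prohibitions during dosing in Section 4.3: 0 of 14. Express permissions: also 0 of 14. No other section closes the gap.

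**3. Where does the rule for verapamil stop protecting?** Section 4.2.6.2 gives 4 antihypertensives for 2 weeks as its example of maximal treatment. A rule against first choice covers position 1 and leaves 4 − 1 = 3 positions open. Until treatment is maximal, the hypertension rules hold axitinib only if two readings within a week exceed 200 systolic or 110 diastolic. Second- to fourth-line drugs can therefore be added while axitinib continues.

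**4. Is verapamil needed?** Section 4.3 names these alternatives: 4 ACE inhibitor or angiotensin agents + 3 beta-blockers + 2 diuretics + 3 other calcium channel blockers = 12, in 4 groups. Overlap with exclusion 5: 0. A 4-drug regimen can be built without verapamil.

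**5. How far does the mismatch reach among antihypertensives?** Four calcium channel blockers are called not first choice. One, verapamil, is on the exclusion 5 list. The other three are not, so for them entry and treatment rules do not conflict.

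**6. What cannot be computed.** The documents give neither the size of the exposure change nor how often a listed inhibitor would be used. No expected number of affected patients can be derived, and zero is possible.

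**The case against.** The strongest reply is that the protocol's intention is already clear. Exclusion 5 implies avoidance on study, and Section 4.3 can be read as the fallback if the combination occurs anyway. This stands in part: what is missing is an explicit sentence, not a policy. But the exclusion is judged at screening, whereas drug-induced hypertension arises later, when the site consults Section 4.3.

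A second reply is that stricter rules at entry than on treatment can be deliberate, leaving a later need for an antifungal or macrolide to clinical judgement, especially as the interaction evidence is preclinical. That is reasonable for anti-infectives, and the fix should preserve that judgement. It is weaker for verapamil, given the 12 named alternatives.

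A third is that the safeguards suffice: daily home readings with call thresholds (Section 3.5.2), two-weekly clinic checks with hold and reduction rules (4.2.6.2), interruption rules for other toxicity (4.2.6.1) and data safety monitoring board review (Section 7). Section 1.2 adds that hypertension at 5 mg BID could always be managed with standard drugs and reversed on stopping. These limit harm and are why the point is small. They do not prevent the combination, and Section 4.2.6.5 lets selected patients escalate to 10 mg BID.

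A reader might go further and take omeprazole as proof that the protocol routinely carries entry bars into treatment, because Section 4.3 says that "patients should not use omeprazole while taking AG-013736 tablets because omeprazole is a CYP1A2 inducer". The documents do not support that. Omeprazole is one of 10 inducers in exclusion 6, and the other nine have no such sentence. The omeprazole note is an exception to the paragraph that allows other antacid drugs with staggered dosing.

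Finally, the protocol refers to an Investigator's Brochure that is not among the documents, and the consent pages were removed. Either may tell sites or patients to avoid these drugs. That would not mend the protocol text, but it limits what can be said about actual instructions.

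**Conclusion.** The point holds as a mismatch between an entry criterion and the on-treatment guidance. Exclusion 5 implies that the 14 inhibitors are to be avoided on study, while Section 4.3 asks only for caution and leaves verapamil open as a later-line antihypertensive. Correcting it is a cheap patient-safety improvement of small and unquantified size.

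Two stronger readings might be inferred and are not supported. Section 4.3 does not authorise the combination; later-line use is an inference from what the text leaves open. Nor is there a basis for expecting an effect on the response rate, the error rates or the sample size.

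The conclusion assumes that sites follow Section 4.3 as written when choosing antihypertensives, and that the preclinical concern which justified the entry bar applies equally during dosing.

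**What to change.** In the antihypertensive paragraph of Section 4.3, state that verapamil is not to be used as an antihypertensive while the patient is taking axitinib. Keep the present wording for nifedipine, nicardipine and diltiazem.

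In the CYP3A paragraph of the same section, state that the inhibitors listed in exclusion 5 are to be avoided during axitinib dosing. If one becomes medically necessary and there is no alternative, the investigator and the medical monitor decide whether to hold axitinib or continue it with closer monitoring. Section 4.2.6.5 already uses this kind of joint decision for dose re-escalation.

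An automatic hold is not advised. The documents give no washout period, and a hold within the 56-day lead-in would shorten exposure before the response scan. No new withdrawal or deviation wording is needed: Section 3.3 concerns permanent withdrawal, and Section 6.2.1 already keeps dosed patients with a baseline assessment in the response analysis.

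The cost is a few sentences in one section. Concomitant medications are already recorded on the CRF, so nothing new has to be collected. The downside is slightly fewer concomitant drug options during dosing.
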